For this protocol, an AE is any "on study" untoward medical occurrence (e.g., sign, symptom, disease, syndrome, intercurrent illness) that is experienced by a study subject, regardless of the suspected cause. Both serious and non-serious AEs will be graded on a three-point scale (mild, moderate, severe), and the investigators will assess whether there is a reasonable possibility that study procedure caused or contributed to the AE.

Adverse events that start on Day 0 (Surgery) through the last study visit will be recorded on the study AE log and described in detail in the patient chart. Subjects discontinued early from the study due to an adverse event will be asked to return for a final evaluation. All study-related adverse events will be followed until resolution (or determined to be irreversible, chronic, or stable).

Adverse events that are determined to be unexpected, possibly related to the study procedure, and place subjects at increased risk, will be reported to the Institutional Review Board (IRB) according to their guidelines.

Standard of Care / Research Costs:

All procedures are considered within the standard of care for PRK surgery and will be billed to patients in the usual manner; however, participants will be eligible for a reduced study fee for their surgery and post-operative care. PRK surgery is considered cosmetic surgery and is never billed to insurance. The refractive surgery charge includes standard post-operative examinations up to one year.

Loteprednol 0.5% gel is not available in a generic formulation and is therefore significantly more expensive than generic prednisolone acetate 1% suspension and fluorometholone 0.1% suspension. A request for a donation of loteprednol 0.5% gel for this study has been submitted to Bausch and Lomb and is currently under review. If approved, this drug donation will allow us to eliminate the additional expense of a branded drug for patients that are randomized to the loteprednol group.

If enhancement surgery is deemed necessary during the one-year post-operative period, this will be included based on the patient's initial fee, as is standard of care. Any other costs related to management of adverse events, or if additional refractive correction is necessary at some time after the one-year postoperative period, will remain the patient's responsibility and are not included in the study surgery fee.

7. Are all procedures for research purposes only (non-standard or non-standard of care procedures)?

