Yes No

If no, list the procedures that are performed for research purposes only (non-standard or non-standard of care procedures):

Only data collection and analysis are for research purposes only. All other procedures are within the standard of care.

8. Is there a safety monitoring plan for this study?

Yes No

9. Provide a summary of the statistical methods, data analysis, or data interpretation planned for this study. Factors for determining the proposed sample size (e.g., power) should be stated.

Standard statistics will be calculated and used to describe the two treatment groups in terms of all study variables: intraocular pressure, grade of corneal haze, manifest refraction, best corrected visual acuity, and uncorrected visual acuity. Statistics will be compiled for each variable at the study time points listed in the data collection protocol. Patients withdrawn from the study prior to surgery will not be included in the data analysis and will be replaced in the enrollment group. For eyes that require enhancement surgery, only data collected prior to the enhancement surgery will be included in the statistical analysis.

Prior studies have considered intraocular pressure elevation of greater than or equal to 10 mm Hg above baseline clinically significant. A prior study of healthy volunteers demonstrated an incidence of IOP elevation > 10 mm Hg of 1.95% in patients using loteprednol eye drops versus 7.48% in patients using dexamethasone eye drops [1]. Using these expected proportions, an alpha of 0.05, and a power of 80%, we would need a sample size of 230 patients (460 eyes). In order to account for about 10% dropout, we intend to enroll 250 patients in the study, 125 in the loteprednol arm and 125 in the prednisolone and fluorometholone arm.

IRB_00075978

Created: 8/9/2014 9:53 AM

IRB_00075978

PI: [name]

Submitted: 8/20/2014

View: 4.2 Consent Process

Title: Efficacy and safety of loteprednol 0.5% gel for routine prophylaxis after photorefractive keratectomy compared to prednisolone acetate 1% suspension and fluorometholone 0.1% suspension

Consent Process

1. The following investigators and internal staff will obtain consent (as indicated on the Study Location and Sponsors Page):

[name] University of Utah

[name]

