IRB_00075978**Created:** 8/9/2014 9:53 AM**IRB_00075978**

View: 6. Risks and Benefits

PI: [name]

Submitted: 8/20/2014

Title: Efficacy and safety of loteprednol 0.5% gel for routine prophylaxis after photorefractive keratectomy compared to prednisolone acetate 1% suspension and fluorometholone 0.1% suspension

6. Risks and Benefits

1. Describe the reasonable foreseeable risks or discomforts to the participants:

This study does not put study participants at any known increased risk beyond that normally assumed by patients undergoing photorefractive keratectomy outside the study, including but not limited to decreased vision, over-correction, under-correction, pain, glare, halos, dry eyes, infection, and corneal haze. The risk of topical steroid-related complications following photorefractive keratectomy, including elevated intraocular pressure, infection, and cataract formation, is assumed by all patients undergoing the procedure at our institution, as it is our routine standard practice to put patients on a tapering regimen of topical steroids post-operatively to decrease the risk of corneal haze.

2. Describe the potential benefits to society AND to participants (do not include compensation):

There may be no direct benefits to participants from their participation in this study. If no difference in efficacy or safety is detected between the two post-operative treatment regimens, this study will support the use of either steroid regimen in patients after PRK. If there is a major difference in the efficacy or safety of these two regimens, this could influence post-refractive surgery treatment practices.

3. Are there any costs to the participants from participation in research?

 Yes No

If yes, specify:

All subjects will be charged the research-discounted price for PRK (\$1200 per eye) and will be responsible for the cost of all necessary medications. Loteprednol is significantly more expensive than prednisolone and fluorometholone. Bausch and Lomb has unconditionally donated loteprednol 0.5% gel for this study, thus patients randomized to the loteprednol arm will be provided this medication without charge. Patients randomized to the prednisolone/fluorometholone arm will be responsible for paying for this medication, just as they would be were they not enrolled in the study.

4. Is there any compensation to the participants?

 Yes No

a. If yes, answer the following:

Specify overall amount:

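### Adverse-event causality and IRB reporting turn on an undefined study procedure rather than the randomised steroid, and logged adverse events are not among the variables described by arm

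*Combined protocol and SAP*

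**What the plan says.** The AE rules are in 4. Study Information, item 6, under Data and Safety Monitoring.

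- **Capture.** An AE is any untoward occurrence "experienced by a study subject, regardless of the suspected cause". "Adverse events that start on Day 0 (Surgery) through the last study visit will be recorded on the study AE log". Every AE is graded on a three-point severity scale.
- **Causality.** For each AE, "the investigators will assess whether there is a reasonable possibility that study procedure caused or contributed to the AE".
- **Follow-up.** "All study-related adverse events will be followed until resolution", or until judged irreversible, chronic or stable.
- **IRB reporting.** This applies to AEs that are "unexpected, possibly related to the study procedure, and place subjects at increased risk".

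Item 9 sets out the analysis: "Standard statistics will be calculated and used to describe the two treatment groups in terms of all study variables". It then names five variables: IOP, haze grade, manifest refraction, best corrected acuity and uncorrected acuity.

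In 6. Risks and Benefits, item 1, the plan recognises "The risk of topical steroid-related complications following photorefractive keratectomy, including elevated intraocular pressure, infection, and cataract formation" and treats that risk as part of routine practice at the institution.

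**The concern.** The steroid regimen is the only thing that is meant to differ between the arms. An AE system that asks about a *procedure*, without saying that the assigned regimen is part of it, directs the investigator to an exposure shared by everyone. Attribution to PRK says nothing about which regimen does more harm.

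The objectives, and 6. Risks and Benefits, item 2, say that finding no difference in efficacy or safety would support using either regimen. If logged AEs are left out of the comparison, that safety conclusion would rest on IOP, haze, refraction and acuity at scheduled visits. Because there is no data and safety monitoring board, and study data and documentation are monitored annually (5. Data Monitoring Plan, item 6), the AE rules carry much of the safety oversight.

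**Working it through.** No figure in the plan bears on this point, so the check is a comparison of the text.

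**1. Which term each rule turns on (item 6)**

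| Rule | Depends on relatedness? | Term used | Assigned steroid named? |
|---|---|---|---|
| Definition, logging, severity grading | No | none | not needed |
| Causality | Yes | study procedure | No |
| IRB reporting | Yes, plus unexpected and increased risk | study procedure | No |
| Follow-up to resolution | Yes | study-related | No |

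Three rules depend on relatedness. Two use *study procedure* and one uses *study-related*. Neither term is defined, and none of the three rules names the regimen.

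**2. What *study procedure* could mean**

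- *PRK surgery.* The term is singular, Day 0 is labelled as surgery, and the monitoring text names treatments separately from procedures. This is the most natural reading. It points to an exposure common to both arms.
- *Everything done in the study, steroids included.* This is possible, because the AE text sits inside the answer to an item asking for all procedures in the project, and that answer describes both regimens. Even so, the rule would give a single judgement that does not separate steroid from surgery.
- *Data collection only.* This is the weakest reading (see the objection).

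On none of these readings is a judgement against the assigned steroid expressly required.

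**3. Named steroid risks against the variables in item 9**

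| Risk named in 6. Risks and Benefits, item 1 | Among the five variables? | Where else recorded |
|---|---|---|
| Raised IOP | Yes, at scheduled visits | AE log |
| Infection | No | AE log |
| Cataract | No | AE log |

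The evaluation schedule in item 6 has no dedicated assessment for infection or cataract. The AE log is therefore the only planned study record of them, and item 9 does not use it.

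**4. Unscheduled visits**

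Item 6 allows extra examinations between study time points but excludes them from the study data. An IOP rise found and managed at such a visit may never appear in the scheduled IOP readings. The AE log could hold it, but that log is not summarised by arm.

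**The case against.** The strongest reply is that capture is complete. AEs are logged and graded regardless of cause, and subjects who discontinue early because of an AE are asked back for a final evaluation. The leading steroid harm, raised IOP, is the primary outcome, measured by a masked examiner and described by arm. A randomised comparison of IOP needs no case-by-case attribution. All of this stands, and it confines the point to attribution and to the harms outside the five variables.

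An investigator could also mark a steroid event as related, since the test is caused or contributed to, and steroid complications are described as a risk of having PRK at this institution. That too stands: the documents show that attribution to the steroid is not expressly required, not that it will never be made.

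Three stronger readings are tempting but unsupported:

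- **The plan limits *study procedure* to data collection.** A reader might infer this from item 7: "Only data collection and analysis are for research purposes only. All other procedures are within the standard of care". That sentence answers a form question about which procedures are done only for research. It does not define the AE term, and on that reading the causality rule would be almost empty.
- **All three relatedness rules share the defect word for word.** They do not. Follow-up uses *study-related*, which in ordinary use could cover the randomised treatment. However, the only relatedness judgement the plan provides is the one against *study procedure*, so that judgement may in practice decide who is followed.
- **Steroid harms escape IRB reporting because of this wording.** For foreseeable harms such as raised IOP, infection and cataract, the requirement that an event be unexpected could exclude them by itself. The wording matters mainly for unexpected steroid events.

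**Conclusion.** The point holds as a gap in attribution and in comparison. Two of the three relatedness rules turn on an undefined term that most naturally means surgery common to both arms. The third turns on another undefined term. Two of the three steroid risks the plan names, and events found at unscheduled visits, enter no planned comparison by arm.

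This rests on two assumptions: that *study procedure* is read as PRK or left to the investigator, and that item 9's list is complete as written. If *study procedure* were read to include the steroids, the attribution gap would narrow to a failure to separate the two causes. The missing AE summary would remain.

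A reader might try to size the problem by applying item 9's IOP-elevation rates to 125 patients per arm. The documents do not support that. The higher rate is for dexamethasone in healthy volunteers, a drug in neither arm, and IOP is already described by arm. No patient count for this gap can be derived from the plan. It does not invalidate the primary outcome, but it should be corrected because the plan intends a general safety conclusion.

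**What to change.** 1. In the causality and IRB-reporting sentences of item 6, replace *study procedure* with two separate judgements: relation to the assigned topical steroid regimen, and relation to the PRK surgery.
2. Define *study-related* as related to either, so that the follow-up sentence clearly covers steroid-related events.
3. In item 9, add AEs by randomised arm: any, severe, steroid-related, and separately IOP elevation, infection and cataract. Take these from the AE log, and state that events first found at unscheduled visits are included. Give most weight to the counts that do not depend on attribution, because the plan describes masking only for IOP measurement and haze grading.

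The cost is a wording change, one extra tick-box on the AE log and one table. Somewhat more events will count as related and need follow-up. Expected steroid effects may still not be reportable to the IRB, because the requirement that an event be unexpected is unchanged. The by-arm table is what brings them into the comparison.

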Desirable characteristics for prophylactic topical steroids to be used after PRK include effective modulation of the healing response to prevent corneal haze while at the same time minimizing side effects, such as intraocular pressure elevation or cataract formation. Loteprednol etabonate is a corticosteroid that exerts its therapeutic effects and is then quickly changed into inactive metabolites by nonspecific esterases found in the cornea [1]. This relatively fast metabolism of loteprednol gives it a lower side effect profile than other steroids, including a smaller effect on intraocular pressure [2, 3]. In the ophthalmic literature, there is currently no consensus on a standard regimen or which type of corticosteroid should be used after PRK.

A retrospective study done at our institution demonstrated a similar incidence of haze and increased intraocular pressure in patients treated with loteprednol 0.5% suspension or fluorometholone 0.1% suspension after both groups received prednisolone acetate 1% suspension for the first 3-4 weeks postoperatively after PRK [4]. This study was limited by its retrospective nature, but was the first study to report the efficacy and noninferiority of loteprednol compared to other steroids for prophylaxis after photorefractive keratectomy. Our current prospective study could help determine whether loteprednol has true advantages over traditional topical steroids after PRK.

References:

4. [name] MD, Leishman LL, Christiansen SM, Sikder S, Hsu M, Moshirfar M. Use of loteprednol for routine prophylaxis after photorefractive keratectomy. Clin Ophthalmol. 2012;6:653-659.

IRB_00075978**Created:** 8/9/2014 9:53 AM**IRB_00075978**

View: 2. Location and Sponsor

PI: [name]

Submitted: 8/20/2014

Title: Efficacy and safety of loteprednol 0.5% gel for routine prophylaxis after photorefractive keratectomy compared to prednisolone acetate 1% suspension and fluorometholone 0.1% suspension

2. Study Location and Sponsors

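### The 80% power is for loteprednol versus dexamethasone in healthy volunteers; power for the trial's own contrast, against prednisolone then fluorometholone after PRK, is not established.

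*Combined protocol and SAP*

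**What the plan says.** 4. Study Information, item 9, treats an IOP rise of 10 mm Hg over baseline as clinically significant and takes both planning rates from one source, a study of healthy volunteers: "1.95% in patients using loteprednol eye drops versus 7.48% in patients using dexamethasone eye drops". The reference given is titled "Effects of loteprednol/tobramycin versus dexamethasone/tobramycin on intraocular pressure in healthy volunteers", so the source products were tobramycin combinations. With these two rates, alpha 0.05 and 80% power, the paragraph arrives at 230 patients, counted as 460 eyes. It then sets enrolment at 250 for dropout: "125 in the loteprednol arm and 125 in the prednisolone and fluorometholone arm".

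The Objectives and item 6 of the same section define the arms. Group 1 receives loteprednol gel only. Group 2 receives prednisolone acetate and is then tapered to fluorometholone. Dexamethasone appears in neither.

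The Background and Introduction describes the institution's own retrospective PRK study, which "demonstrated a similar incidence of haze and increased intraocular pressure in patients treated with loteprednol 0.5% suspension or fluorometholone 0.1% suspension", after both groups had taken prednisolone for the first 3-4 weeks. It gives no rate, denominator or definition of raised IOP.

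The Objectives and 6. Risks and Benefits, item 2, both say that if no difference in efficacy or safety is detected, the study will support using either regimen. No equivalence or non-inferiority margin is stated.

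**The concern.** A power statement describes a trial only if its assumed rates are plausible for that trial's arms. Here the control rate belongs to another drug, given to people who were volunteers rather than PRK patients. The documents contain no bridging argument, no rate for the actual control regimen and no sensitivity range.

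The consequence lies in how the result will be read. The plan intends to draw a positive conclusion from a null finding and sets no margin for doing so. A reader looking for reassurance that an important difference in IOP rises would have been found has only the 80% figure to rely on. If the true rates are closer together than 1.95% and 7.48%, a non-significant comparison could be the likely result even though a real difference exists, and the 80% would be cited in its support.

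**Working it through.** **Inputs.** Loteprednol rate p1 = 0.0195, comparator rate p2 = 0.0748, alpha 0.05, power 80% and 1:1 allocation, all from item 9. Sidedness is not stated; two-sided is assumed because it reproduces the plan's number.

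**Step 1: reproduce the plan's figure.** Pooled two-proportion formula, no continuity correction, with p̄ = (p1 + p2)/2:

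n per arm = [1.960·√(2p̄(1−p̄)) + 0.842·√(p1(1−p1) + p2(1−p2))]² / (p2−p1)²

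- p̄ = 0.04715 and √(2p̄(1−p̄)) = 0.2998
- √(p1(1−p1) + p2(1−p2)) = 0.2972
- Numerator: (0.5875 + 0.2501)² = 0.7016
- Denominator: 0.0553² = 0.003058
- n = 229.4, rounded up to 230 per arm, 460 in total

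This matches the plan's 460 when the unit is the eye. Power at 230 per arm is 80.1%. The calculation is sound for the contrast it describes.

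**Step 2: vary the rates.** The documents give no IOP-rise rate for prednisolone then fluorometholone, so no single corrected power can be derived. The ranges below are assumptions. With n = 230 per arm:

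Power = Φ{ [√n·(p2−p1) − 1.960·√(2p̄(1−p̄))] / √(p1(1−p1) + p2(1−p2)) }

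Worked case, control 5% and loteprednol 1.95%: p̄ = 0.03475; (0.4626 − 0.5076)/0.2581 = −0.175; Φ(−0.175) = 43%.

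| Control rate | Loteprednol 1% | Loteprednol 1.95% | Loteprednol 3% |
|---|---|---|---|
| 4% | 54% | 25% | 8% |
| 5% | 71% | 43% | 19% |
| 6% | 83% | 60% | 34% |
| 7.48% | 93% | 80% | 58% |
| 9% | 98% | 92% | 78% |

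Power moves both ways and depends on the loteprednol rate as much as on the control rate. If both planning rates were 1.5 times higher (2.93% and 11.22%), it would be 94%.

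**Step 3: is there a better rate in the documents?** The retrospective PRK study had a group on prednisolone then fluorometholone, the same type of regimen as this trial's control arm. It is the closest source cited, but the documents report no rate from it and do not say how raised IOP was defined. Its prednisolone phase lasted 3-4 weeks, whereas item 6 gives no duration for that phase in this trial. Whether its rate can be used depends on information outside the documents.

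**The case against.** The strongest reply is that the plan hides nothing. It names the drug, the population and the source, and presents the sample size as following from those expected proportions. Planning rates are often borrowed, and a power figure is always conditional. That is fair as far as it goes, but a borrowed rate needs some stated reason to apply to the arm it represents, and none is given.

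Three stronger readings are tempting and are not supported.

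- **That the retrospective study shows the power is wrong because it found similar IOP rates.** Both of its groups took prednisolone first, so any effect of that phase was common to them. It compared only the later phase, loteprednol suspension against fluorometholone. This trial compares loteprednol gel throughout with prednisolone then fluorometholone.
- **That true power must be below 80%.** Nothing in the documents puts the control rate under 7.48%. Item 6 schedules six postoperative IOP measurements over a year with a taper guided by judgement, so a higher cumulative rate cannot be excluded, and power would then be higher.
- **That power is really 51%, the value at 115 per arm with the plan's own rates.** That fall comes from treating the patient rather than the eye as the unit, with fellow eyes fully correlated. It is a separate issue and has nothing to do with the choice of comparator.

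Two further points stand in part. Reading a null result as support for either regimen would be unsound at any assumed rate; the unsupported power makes it worse but does not create it. Also, the stated primary outcome is IOP at each time point, so these figures concern the proportion with a 10 mm Hg rise and do not predict the result of the primary comparison.

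**Conclusion.** The point holds in this form: the 80% belongs to loteprednol versus dexamethasone in healthy volunteers, and power for the trial's own contrast is not established. The size of the uncertainty is large. With loteprednol at 1.95% and 230 independent eyes per arm, a control rate anywhere from 4% to 9% gives power from 25% to 92%. At a 5% control rate, moving loteprednol between 1% and 3% shifts power from 71% to 19%. These figures rest on a two-sided 5% test, the pooled normal approximation, the plan's counting of eyes as independent, and assumed rates; the documents support no particular value within the range. The point should be addressed because the plan attaches a conclusion to a null result, and the stated power cannot carry that conclusion.

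**What to change.** 1. In 4. Study Information, item 9, state that the 80% applies only to 1.95% versus 7.48%, rates seen with loteprednol and dexamethasone in healthy volunteers, and that no rate for prednisolone then fluorometholone was used.
2. Add a short table of power, or of the smallest detectable difference, at the fixed enrolment of 250. Vary both rates in both directions and state the unit of analysis. With 10% dropout, 250 × 0.9 = 225 patients, or 225 eyes per arm on the plan's counting; power at the planning rates is then 79%, so the table above changes little.
3. Use the rate from the prednisolone-then-fluorometholone group of the institution's retrospective study only if it can be put on the same 10 mm Hg definition. Otherwise, say that no suitable rate is available.
4. State that the difference in IOP-rise proportions will be reported with a confidence interval.
5. Amend the Objectives and 6. Risks and Benefits, item 2, so that a non-significant result is not read as equal safety, and the conclusion rests on which differences the interval excludes.

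The cost is rewording of three short passages and one small table. No patients, visits or measurements are added. The plan gives up an unconditional power claim and the automatic reading of a null result.

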Prior to surgery, patients will be randomly assigned to one of two postoperative steroid regimens. Group 1 will use loteprednol 0.5% gel in both eyes, starting at a frequency of four times per day for the first week and then tapered off based on clinical judgement of the corneal healing response. Group 2 will use prednisolone acetate 1% suspension in both eyes, starting at a frequency of four times per day for the first week, then tapered down to a regimen of fluorometholone 0.1% suspension, which will then be tapered off based on clinical judgement of the corneal healing response.

All surgical procedures will be performed according to the standard of care and the surgeons' standard practices. The study outcome measures are standard of care for pre-operative and post-operative evaluation of refractive surgery patients.

The primary outcome measure will be intraocular pressure at each study time point. Secondary outcomes will be grade of corneal haze, manifest refraction, best corrected visual acuity, and uncorrected visual acuity.

Study outcome measures will be evaluated for each treated eye of each subject at each study time point. Routine clinical management may be altered if the intraocular pressure is elevated sufficiently to require medical intervention, if there is significant postoperative corneal haze, or if there are other postoperative complications. In these situations, additional IOP lowering drops may be added or the steroid decreased, changed, or increased, based on the clinical picture and physician judgement. Additional examinations between study time points may be performed as necessary according to the surgeon's usual care, but will not be considered part of the study data. Patients have the right to withdraw at any time and future medical care will not be influenced by their lack of participation.

If enhancement surgery is deemed necessary and performed during the one-year post-operative period, study data collection will end for that eye at the time of the enhancement. All prior data collected will still be included in the statistical analysis and if only one eye requires enhancement, data collection will continue on the fellow eye until the last planned study time point.

Eyes will be evaluated with the following procedures:

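### The 80% power for 230 patients counts both eyes of 115 patients per arm as independent units; for the 10 mm Hg IOP-elevation endpoint it holds only if between-eye correlation is near zero

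*Combined protocol and SAP*

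**What the plan says.** Item 9 of section 4 (Study Information) takes the incidence of an IOP rise of more than 10 mm Hg from a study in healthy volunteers: "1.95% in patients using loteprednol eye drops versus 7.48% in patients using dexamethasone eye drops". From these rates it concludes that with "an alpha of 0.05, and a power of 80%, we would need a sample size of 230 patients (460 eyes" the trial is adequately sized. Allowing for dropout, "we intend to enroll 250 patients in the study, 125 in the loteprednol arm and 125 in the prednisolone and fluorometholone arm".

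Item 6 of the same section fixes the design. "Prior to surgery, patients will be randomly assigned to one of two postoperative steroid regimens", and the regimen applies to both eyes; for example, "Group 1 will use loteprednol 0.5% gel in both eyes". Measurement is by eye: "Study outcome measures will be evaluated for each treated eye of each subject at each study time point". Follow-up can also differ between the two eyes of a patient, since "if only one eye requires enhancement, data collection will continue on the fellow eye until the last planned study time point". Item 9 carries this into the analysis: "For eyes that require enhancement surgery, only data collected prior to the enhancement surgery will be included in the statistical analysis".

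On method, item 9 promises only standard statistics for each variable at each time point. The documents give no between-eye correlation, design effect, analysis clustered by patient, one-eye rule or patient-level definition of the event.

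**The concern.** Two eyes of one patient share the drug, the surgery and the patient's own steroid response. They are a cluster of two within one arm and carry less information than two patients unless their outcomes are uncorrelated. If the calculation treats 460 eyes as 460 separate units, the real power is below the stated 80%.

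The power figure bears on how a null result is read. The Objectives, and item 2 of section 6 (Risks and Benefits), say that finding no difference will be taken as support for using either regimen. That inference is weaker if a true difference of the planned size is missed more often than the implied 20% of the time. The unit of the borrowed rates adds to the problem: item 9 words them as rates in patients but spends them on eyes.

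**Working it through.** **Inputs.** From item 9: p1 = 0.0195, p2 = 0.0748, alpha 0.05, power 80%, 230 patients (460 eyes), 1:1 allocation, hence 115 patients or 230 eyes per arm. From item 6: randomisation by patient, both eyes on the same regimen. Assumed, because the documents give no value: between-eye correlation ρ from 0 to 1, equal in both arms.

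**Step 1: reproduce the plan's figure.** The pooled two-proportion formula per arm is

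n = [z(α/2)·√(2·p̄·q̄) + z(β)·√(p1·q1 + p2·q2)]² / (p2 − p1)²

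with p̄ = (0.0195 + 0.0748)/2 = 0.04715 and q̄ = 0.95285.

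- √(2 × 0.04715 × 0.95285) = 0.2998
- √(0.01912 + 0.06920) = 0.2972
- n = (1.960 × 0.2998 + 0.8416 × 0.2972)² / 0.0553² = 229.4, so 230 per arm and 460 in total.

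The plan does not state sidedness. Two-sided is inferred, because one-sided 0.05 gives 180.6 and does not return 460. Continuity-corrected, unpooled and arcsine variants were also tried. None gives 115 units per arm, so no patient-level version of the calculation leads to 230 patients. The 460 units are eyes.

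**Step 2: allow for pairing.** With m patients per arm and two eyes each, the design effect is 1 + ρ and the effective number of units per arm is 2m/(1 + ρ). Power by the plan's own formula is

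Φ{[0.0553·√n − 1.960 × 0.2998] / 0.2972}.

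Example at ρ = 0.3 and m = 115: n = 230/1.3 = 176.9; (0.0553 × 13.30 − 0.5875)/0.2972 = 0.498; Φ = 0.691.

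The simulation column uses paired binary eyes, 200,000 trials per scenario and a score-type test of the risk difference clustered by patient, with m = 115.

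| Assumed ρ | Effective units per arm | Power, formula | Power, simulation |
|---|---|---|---|
| 0 | 230.0 | 80% | 83% |
| 0.1 | 209.1 | 76% | 80% |
| 0.3 | 176.9 | 69% | 72% |
| 0.5 | 153.3 | 63% | 66% |
| 0.8 | 127.8 | 55% | 58% |
| 1.0 (limit) | 115.0 | 51% | 51% |

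**Step 3: the other unit.** If 1.95% and 7.48% are patient-level rates, there are 115 units per arm and the last row applies: about 51%.

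**Step 4: ignoring the pairing.** With a common rate of 4.7% and 115 patients per arm, a test that treats eyes as independent has a simulated type I error of 8.3% at ρ = 0.3 and 10.9% at ρ = 0.5. The clustered test stays at 4.5-5.3%.

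**The case against.** The strongest reply is that the shortfall is conditional. No document gives a correlation, so none of the values above zero is established. If all 125 enrolled patients per arm are analysed, the simulated power of the clustered test is 82% at ρ = 0.1 and still about 80% at 0.15. This stands: the size of the loss is unknown. It does not rescue the paragraph, which states 80% without condition. With 125 per arm, power is still 73-76% at 0.3 and 66-70% at 0.5.

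Second, item 6 makes IOP at each time point the primary outcome, and item 9 uses the 10 mm Hg threshold only for sizing. This also stands and limits the point. Nothing here shows low power for IOP at each time point, or for haze, refraction or acuity, although the statement about finding no difference covers efficacy and safety together.

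Third, power depends on the test. The simulated values belong to a score or identity-link test of the risk difference. A logit-link GEE with a robust Wald test has only about 66%, 57%, 43% and 35% at ρ = 0.3, 0.5, 0.8 and 1.0, counting trials with a zero-event arm as non-significant. So the range must not be attached to clustered methods in general.

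Fourth, a patient-level event of elevation in either eye might seem a way out. With per-eye rates, its probability is 2p − p² − ρp(1 − p), and the formula with 115 per arm gives about 80%, 73%, 67%, 58% and 51% at ρ = 0, 0.3, 0.5, 0.8 and 1.0. It does not restore 80% either.

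A reader might go further and infer that true power is about one half, that the trial will produce inflated false positives, or that enrolment must rise. The documents do not support these. The 51% needs either perfect correlation or patient-level rates, and neither is established. The plan names no test, so the type I error figures describe a possible analysis and not a planned one. Whether to restore 80% by recruiting more is a choice for the investigators.

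**Conclusion.** The 80% is wrong as written, because it is stated without the condition on which it depends. The figure of 230 per arm is a number of independent units, and the plan supplies it as 230 eyes from 115 patients. For the 10 mm Hg IOP-elevation endpoint, 80% is roughly kept up to a correlation of about 0.1 (76% by the plan's formula, 80% by simulation) and is lost at moderate or higher values. A difference of the planned size would be missed about 28-31% of the time at 0.3 and 34-37% at 0.5.

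The unit count is firm. The size of the loss rests on the assumed correlation (the same in both arms), an inferred two-sided alpha, 115 evaluable patients per arm, per-eye rates and the clustered risk-difference test. The statement should be corrected because it is the only power basis in the plan and a null result is to be read as support for either regimen.

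**What to change.** Keep enrolment at 250 and restate the sample-size paragraph in item 9 along these lines, choosing one option in the brackets:

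> Detecting 1.95% versus 7.48% with 80% power at two-sided alpha 0.05 requires 230 independent units per arm. The rates are taken as [per-eye / per-patient] rates. Both eyes of a patient receive the same regimen. With 115 evaluable patients per arm and per-eye rates, power for the 10 mm Hg IOP-elevation endpoint is about 76-80%, 69-72%, 63-66% and 55-58% at assumed between-eye correlations of 0.1, 0.3, 0.5 and 0.8, and 51% in the limiting case of 1.0 (lower value: normal approximation; upper value: simulation). [If per-patient: power is about 51%.] This endpoint will be analysed as an eye-level risk difference, tested with a patient-clustered score test and reported with a 95% confidence interval.

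An identity-link model with robust variance is an acceptable alternative to the score test. For any other test, including a logit-link GEE with a Wald test, compute the power for that test and do not borrow this range. If the rates are declared per-patient, the named analysis should use one outcome per patient. The conclusions about finding no difference, in the Objectives and in item 2 of section 6, should then be read against the confidence interval.

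The cost is one reworded paragraph and a less favourable power statement. No extra patients, visits or measurements are needed.
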